4.0 Study Endpoints

Type	Endpoint	Time Frame	Brief Description
Primary	Brain Metabolites	Visit 1 and Visit 2	MRS quantifies metabolites in the brain, including glutamate and GABA levels, which are affected by substance use and are therefore targets for substance use medication development ⁷⁹⁻⁸¹ .
Primary	fMRI Alcohol Cue-Reactivity	Visit 1 and Visit 2	fMRI localizes and quantifies brain activity, allowing for mechanistic understanding of neural substrates affected by the candidate medication. fMRI cue reactivity tasks activate incentive salience and reward circuitry ⁸³ , and these cue-related brain activation patterns have been modulated by pharmacological intervention; predicted later relapse; and are associated with alcohol craving ⁸⁴
Primary	Psychophysiological cue reactivity	Visit 1 and Visit 2	Cue reactivity can also be assessed during an olfactory cue reactivity task (measured via heart rate, skin conductance, and subjective ratings) ⁸⁵ to better understand psychophysiological effects of potential medications.

5.0 Inclusion and Exclusion Criteria/ Study Population

Youth (ages 16-22; 50% women) alcohol users (N=50) will be recruited for the current study. To promote consistency between human laboratory models and clinical trials, we will recruit youth who meet criteria for AUD (≥ 2 symptoms)¹⁰². At the end of the trial, all participants will have the opportunity to meet with a trained clinician for a brief treatment session from NIAAA's brief alcohol intervention, which includes motivational interviewing and setting individual goals and action plans, consistent with the current standard-of-care treatment. We will also offer referral to additional clinical services, as well as provide all participants with a handout listing all community mental health and substance use programs.

Participants having completed a separate ongoing research study (PRO #94743) who have consented to future contact and meet study criteria will be offered participation.

Inclusion Criteria

- (1) ages 16-22
- (2) participants ages 16-17: a parent or legal guardian must be able to provide informed consent and youth must be able to provide assent
- (3) participants ages 18-22: must be able to provide informed consent
- (4) AUD in the past year and at least one current (past 30 days) continued symptom besides craving

- (5) have used alcohol in the past two weeks before screening.

Exclusion Criteria

- (1) significant or acutely unstable medical, psychiatric, or substance use problems (e.g., current manic episode, positive psychotic symptoms, severe eating disorder, severe opioid use disorder) that would contraindicate research procedures, interfere with safety, compromise data integrity, or preclude consistent study participation
- (2) significant risk of homicide or suicide
- (3) currently enrolled in or acutely seeking treatment for AUD or any other SUD
- (4) pregnant, trying to become pregnant, or breastfeeding
- (5) known allergy or intolerance to CBD
- (6) current use of CBD or any supplement containing CBD
- (7) history of a serious medical or neurological problem that could affect neural response or brain development
- (8) non-correctable visual or hearing problems
- (9) MRI contraindications (e.g., braces, claustrophobia, irremovable metal implants or piercings)
- (10) acute drunkenness or consumption of alcohol within 12 hours of visit
- (11) ≥ 10 on the Clinical Institute Withdrawal Assessment for Alcohol (CIWA)
- (12) severe Cannabis Use Disorder (CUD)
- (14) concurrent medications with potential drug-drug interactions with CBD, including CYP3A4 and CYP2C19 substrates, inhibitors, and inducers, as well as CYP2C8/9 substrates.

Age Range: This work emphasizes capturing neurobehavioral effects of CBD during early life AUD, which will require a broad age range as drinking habits and consequences can widely vary among youth, while limiting neural and AUD heterogeneity within the sample. The CDC defines adolescence as ages 10-24. While some youth initiate alcohol use before age 16, few meet criteria for AUD¹⁰³. Therefore, we chose a lower age limit of 16 and upper limit of 22 to reduce heterogeneity, while still sampling across the period when substance use problems emerge and peak. We will complete exploratory analyses within age and education-level subgroups to probe the confounding effect of developmental heterogeneity. Creation of alcohol-focused interventions during adolescence could have substantial long-term implications by reducing acute and long-term negative social, academic, and cognitive consequences related to heavy teen drinking and by reducing the rate of youth transitioning from heavy drinking to more problematic alcohol dependence. While participants in this study are not treatment seeking, all participants will be given treatment referrals at the conclusion of the study.

Diverse Population: In this cohort, approximately 50% of the participants will be female, and we aim to recruit participants to approximate the racial and ethnic composition of Charleston County.

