10.0 Study Design / Methods

Entryway Intake. All participants will complete a centralized Entryway Intake process for substance use studies at MUSC (i.e., the Entryway Intake (PRO #94743)) to determine eligibility before consenting for this project. This triaged approach allows for minimization of participant study shopping ("professional participants") and assurance that participants are triaged to the most appropriate study, thereby increasing the confidence and validity of study-specific results¹⁰⁴⁻¹⁰⁶. Eligibility criteria for all Youth Collaborative studies (including the proposed study) will be concurrently assessed during the Intake and participants will only be offered study participation in studies for which they are eligible.

Overview. Our primary goal is to test CBD as a potential candidate medication for youth with AUD, leveraging neuroimaging and behavioral data, to examine the acute neurometabolic, neurobehavioral, and psychophysiological effects. In counterbalanced order, youth (ages 16-22; 50% female) will receive 600 mg of CBD²⁵⁻³⁰ or matched placebo with a standardized snack, separated by approximately 18 days³¹ (see Figure below). We will stratify by education level (high school vs post high school) to ensure that these developmental groups are represented equally between the randomized crossover orders within our final sample. Neuroimaging will be collected after each medication trial: MRS will examine glutamate and GABA levels in the anterior cingulate cortex, and fMRI alcohol cue reactivity will examine neural response in reward networks, post-CBD and placebo. *In vivo* response to olfactory alcohol cues will be measured via heart rate, skin conductance, and subjective ratings⁸⁵.

Participant Procedures

CBD or placebo administration. This double blind crossover trial will compare acute oral CBD (600 mg^{25-27,29}) and placebo, followed by an approximate 18 day washout to allow for CBD clearance³¹ (terminal half-life 18-32 hours after acute oral dose)⁹³. All participants will eat a standardized snack with each medication administration. Neuroimaging will be conducted 3 hours after CBD/placebo administration to allow for CBD to reach its peak plasma concentration^{26,101}. Medication response and tolerability/adverse events will be assessed at each visit.

Assessments

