Crossover designs are highly cost-efficient and powerful designs¹¹². Laboratory studies can enroll more participants and minimize statistical noise through greater experimental control³². The primary outcome measures of interest will be glutamate and GABA levels (MRS; Aim 1), alcohol cue reactivity (fMRI; Aim 2), and *in vivo* response to olfactory alcohol cues (heart rate, skin conductance, subjective rating; Aim 3). For all outcomes, a generalized linear mixed effects regression model will be developed accounting for clustering within subject. Additionally, study day (scan 1 vs. scan 2), condition (CBD vs. placebo), and condition order (CBD/placebo, placebo/CBD) will be included to ensure the crossover design and washout period were successful. During model development, random intercepts will be included to account for variations in baseline response levels for individual participants and random slopes to account for varying responses to treatment. For all models, baseline characteristics will be assessed for association with study outcomes (e.g., sex, baseline alcohol use rates, alcohol craving) and when significant, will be added in a covariate adjusted model. Model based interactions will assess any differential effect of sex on the relationship between medication condition and study outcomes.

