Power and sample size. The proposed study is primarily powered to assess the relationship between treatment with CBD as compared to placebo on glutamate and GABA levels in the anterior cingulate (Aim 1) and neural response to alcohol cues (Aim 2). In a cross-over study of the effects of CBD as compared to placebo on glutamate in the hippocampus in a population of patients with schizophrenia, significant increases were found ($d= 0.48$; $p=0.035$)²⁵. To our knowledge, the effects of CBD on cue reactivity have not been assessed using fMRI. However, several studies have demonstrated that CBD can modulate resting-state^{28,29} or task-based^{5,27,30,113-116} BOLD signal under similar study design (acute dosing, 600 mg CBD) with sample sizes smaller than our proposed sample. Given limited literature in this area, we were not able to run a power analysis for Aim 3; this pilot study will provide data to power further analyses/effect sizes. Due to the number of tests run within the fMRI and MRS aims, the study will be powered at 80% with a corrected $\alpha=.0005$ (.05/100). Thus, in a crossover randomized controlled trial, **n=27 study completers** would be necessary. Although the proposed project is of relatively short duration (1.5 months), we anticipate an attrition rate of up to 7 participants (~23%) due to head motion or other artifacts, thus requiring a total of **n=50 participants enrolled and randomized**.

Rigor and Transparency. The proposed study is rigorous and will achieve robust and unbiased results by using explicit inclusion/exclusion criteria (commensurate with AUD trials for youth); use of validated measures and methods; explicit hypotheses and corresponding planned statistical analyses; power estimates; planned handling of retention/attrition and missing data; and careful consideration of potential

confounds. Key biological variables such as sex and age are considered and are incorporated into the proposed data analytic plan. All experimental details are reported in a detailed and fully transparent manner for replication.

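### No stated analysis tests whether the CBD effect differs by age or education: the plan analyses within those subgroups and gives an interaction for sex only (minor)

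*Combined protocol and SAP*

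**What the plan says.** Section 5.0 (Age Range) sets the limits at 16 and 22 and then adds: "We will complete exploratory analyses within age and education-level subgroups to probe the confounding effect of developmental heterogeneity". It gives no age cut-point, significance level or rule for interpreting the results.

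Section 10.0 (Overview) makes education a randomisation stratum: "We will stratify by education level (high school vs post high school"). The purpose given is to balance the two crossover orders within each level. Nothing fixes how many participants fall in each level.

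Section 12.0 (Data Analysis) describes a mixed model with study day, condition and condition order. Baseline characteristics associated with an outcome are added as covariates; the examples are sex, baseline alcohol use and craving. The only treatment interaction is for sex: "Model based interactions will assess any differential effect of sex on the relationship between medication condition and study outcomes".

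Section 12.0 (Rigor and Transparency) then says: "Key biological variables such as sex and age are considered and are incorporated into the proposed data analytic plan". No age term, as a main effect or an interaction, is named in Data Analysis.

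**The concern.** Each participant is compared with themselves about 18 days apart, so age and education are essentially the same at both scans. They cannot confound the CBD–placebo contrast in complete pairs, although section 5.0 speaks of confounding. What remains is whether the size of the CBD effect depends on developmental stage, which is an interaction. The plan uses an interaction for sex and, without giving a reason, not for age or education.

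Analysing each subgroup separately yields two results but no estimate of the difference between them. A reader who sees one p-value below the threshold and one above it may infer a developmental difference that the data do not show. There is ample room for this. Six outcomes (glutamate, GABA, fMRI cue reactivity, heart rate, skin conductance, subjective rating), two factors and at least two levels each make 6 × 2 × 2 = 24 or more within-subgroup analyses. The study is meant to inform a larger trial, so a spurious age or education pattern could affect that trial's population.

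**Working it through.** **The plan's own figure.** The documents give none for the subgroup analyses. The 27 completers in Power and sample size do not follow from d = 0.48 and alpha 0.0005: ((3.481 + 0.842)/0.48)² = 81.1, so 82 two-sided. That is a separate matter. Here 27 serves only as a lower bound on the number analysed.

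**Inputs.**
- d = 0.48, the only effect size given (section 12.0, hippocampal glutamate in schizophrenia). Assumption: it is the standardised paired difference.
- Two-sided 0.05. Assumption, because no alpha is stated for these analyses. The powering alpha of 0.0005 is the alternative.
- Number analysed: 50 (all enrolled), 43 (50 − 7 lost) or 27 (required completers).
- Splits: near-equal, plus 29+14 and 32+11 of 43. Assumption, because stratum sizes are not fixed.
- The true effect is identical in both groups.

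**Formula.** Let p1 and p2 be the paired-t power in each group (noncentral t). Then P(exactly one significant) = p1(1 − p2) + p2(1 − p1).

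| Split | p1 | p2 | Exactly one significant |
|---|---|---|---|
| 25+25 | 0.634 | 0.634 | 2 × 0.634 × 0.366 = 46% |
| 22+21 | 0.575 | 0.553 | 0.575 × 0.447 + 0.553 × 0.425 = 49% |
| 14+13 | 0.384 | 0.357 | 0.384 × 0.643 + 0.357 × 0.616 = 47% |
| 29+14 | 0.704 | 0.384 | 0.704 × 0.616 + 0.384 × 0.296 = 55% |
| 32+11 | 0.749 | 0.302 | 0.749 × 0.698 + 0.302 × 0.251 = 60% |

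Reading the attrition as 23% of 50 leaves 38.5. A 20+19 split has powers 0.531 and 0.508 and gives 0.531 × 0.492 + 0.508 × 0.469 = 50%.

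**Interaction test in the same setting.** In 40,000 simulated trials per split, a two-group test on the within-person differences was significant at two-sided 0.05 in 5.0% (25+25), 5.1% (22+21) and 5.0% (14+13). Simulated discordance was 46%, 49% and 47%.

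**Sensitivity to the inputs.**
- True effect, 22+21 at 0.05: d = 0 gives 2 × 0.05 × 0.95 = 9.5%; d = 0.2 gives 25%; 0.3 gives 39%; 0.6 gives 37%; 0.8 gives 11%.
- Alpha 0.0005 at d = 0.48: 16% (25+25), 11% (22+21), 4% (14+13), 16% (32+11). The smaller alpha is not protective in general: at d = 0.8 with 22+21 it gives 47%.
- For two groups of equal power, 2p(1 − p) cannot exceed 50%. The 46–49% is therefore close to the equal-split maximum.

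**Power of the interaction.** The difference detectable with 80% power is (1.96 + 0.8416) × √(2/n), in SDs of the within-person difference. This is 0.79 with 25 per group, 0.86 with 21 and 1.10 with 13. With 21 per group the 95% interval is about ±1.96 × √(2/21) = ±0.60 SD.

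**The case against.** The strongest reply is that the plan promises only exploratory analyses. It does not say that significance in one group will be set against non-significance in the other, and subgroup estimates with intervals would also fit the text. This stands: the error rate belongs to one natural reading of the output, not to a rule in the plan.

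It also stands that the 46–49% needs a nominal 0.05, a near-equal split and an effect borrowed from another brain region and patient group. A reader might infer that a false one-group-only result appears about half the time whatever the truth. The documents do not support that, and the range above shows why.

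Two further inferences fail. A reader might take the subgroup check to be the justification for the 16–22 range. Section 5.0 instead rests the limits on how few youth meet AUD criteria before 16, on limiting heterogeneity and on covering the years when problems emerge and peak. A reader might also say that the plan throws away its stratification factor. Education is one of the named subgroup factors, the covariate list is open-ended, and an education main effect would not alter the within-person contrast in complete pairs.

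Finally, the interaction test is weak at this sample size, and a non-significant result could be misread as homogeneity. That is true and must be disclosed. It does not rescue the separate analyses, which use the same data and leave the uncertainty about the difference unreported.

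**Conclusion.** The point holds as a minor one. The plan raises a developmental question and states no analysis that answers it: the interaction is for sex only, and the statement that age is incorporated has no counterpart in the model description.

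At d = 0.48 (as a paired standardised difference), two-sided 0.05 and identical true effects, separate analyses disagree on significance in 46–49% of trials for the 25+25, 22+21 and 14+13 splits, and in 55–60% for the two unequal splits. An interaction test errs in 5%. With other true effects at 22+21 and 0.05 the figure is as low as 9.5%, and with alpha 0.0005 at d = 0.48 it is 4–16%. The case does not depend on any one of these numbers, because separate subgroup results do not estimate the difference under any of them. The primary CBD–placebo contrast is unaffected.

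**What to change.** In section 12.0 (Data Analysis), replace the within-subgroup analyses with exploratory condition-by-education and condition-by-age terms in the mixed model already described, with age continuous so that no cut-point is needed. Age and education will overlap heavily between 16 and 22, so fit the two interactions in separate models. Report each interaction estimate with its confidence interval, and show subgroup effects only as descriptive output of the same model. Amend the sentence in section 5.0 to match, and describe the aim as effect modification, not confounding.

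State the limitation beside the results: 80% power needs an effect difference of about 0.86 SD with 21 per education group, so a non-significant interaction must not be read as a homogeneous effect.

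The cost is a change of wording. It needs no new data, visits or participants, and it would make the claim in Rigor and Transparency about age agree with the model.

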6.0 Number of Subjects

We propose to enroll 50 participants.

7.0 Setting

Visits will take place at MUSC in the Institute of Psychiatry, Roper Office Medical Building, and the Biomedical Imaging MRI research facility at [name] (for those visits requiring an MRI). If a participant is

unable to attend or complete a visit due to unexpected conflict (e.g., transportation issues, travel, University closings), arrangements may be made to remotely complete as much of the visit procedures as possible to maintain data collection and study engagement. This will be done via Zoom and REDCap assessments.

8.0 Recruitment Methods

All participants will be recruited from a pool of participants who have completed an ongoing Entryway Intake study (PRO #94743). Participants who have completed this protocol and who appear to meet eligibility criteria will be offered participation in this protocol. Individuals who participate in the Entryway Intake consent for their data to be carried forward into the study in which they ultimately enroll. The Entryway Intake includes, but is not limited to, a comprehensive substance use history assessment and a structured diagnostic interview for psychiatric conditions, including assessment of AUD and other substance use disorders, as well as bioassay collection. After completion of the Entryway Intake, participants who are eligible for the current study will be offered participation. They will consent to sharing data collected across both protocols for analysis. Since launching the shared Entryway Intake in September 2020, we have averaged 33 referrals per month of youth (ages 16-22) interested in participating in alcohol studies. In the past 10 months, we have had 74 youth in this age range complete our shared Intake process. Of the total intakes, 41 (55%) met criteria for AUD, of which 20 (49%; 2/month) met for moderate or severe AUD. This is consistent with our proposed recruitment rate of 1.8/month. Study staff may also use the following methods of advertising to promote recruitment: local publications, physician offices/local clinics, MUSC campus, local college and high school campuses as permissions are granted by the academic institution, internet, social media, TV commercials, and other locations (e.g., restaurants, movie theaters, malls, buses/transportation services) in the community that agree to post Brand and IRB approved recruitment materials for this study and that may reach our target population.

Our team has been successful with optimizing participant retention via several well-established strategies. We maintain active communication with participants between visits via their preferred mode of contact (e.g., text message, e-mail). We strictly maintain confidentiality, a particularly significant issue in studies focused on youth substance use interventions, and our team has extensive experience in managing communication with study participants while maintaining appropriate bounds of confidentiality and managing issues of safety; the resultant trust and rapport supports participant adherence and retention.

9.0 Consent Process

Prior to the initiation of any study procedures, the MUSC Institutional Review Board (IRB) written and approved Informed Consent (IC) and HIPAA authorization will be obtained by IRB-approved, trained, designated research staff in a private interview room. Potential participants (and parents/guardians, as appropriate) will be provided with a copy of the IRB-approved consent form prior to their visit. After the Entryway Intake and prior to initiating any specific study procedures, research staff will obtain written informed consent and provide a copy of HIPAA privacy practices to potential participants. Parents/guardians will participate in the informed consent/assent procedures for youth between the ages of 16-17. Participants 18 years and older will provide their own informed consent. The complex issues of informed consent and assent, and related limitations of confidentiality, as they apply to youth and their parents/guardians, are understood by the research team and will be communicated clearly during the visit. Trained research staff members complete online and lab-based training in HIPAA policy, human subjects' research, and management of other research issues. During the consent phase, participants and parents are informed that all information provided is confidential within ethical and legal limits to facilitate disclosure. During the consenting process, parents are told that they will not be informed about their child's substance use and that youth self-report and lab data are confidential, except for any acute safety issues (e.g., suicidality, abuse). After given the chance to answer any questions concerning the study, individuals who agree to participate will be asked to sign the informed consent form. As part of the informed consent procedures, participants will be asked to provide or decline consent to be contacted for future studies. The forms are reviewed with the interested parties and filed in a locked file cabinet in a locked office. Trained research staff members complete online and lab-based training in HIPAA policy, human subjects' research, and management of other research issues.

We may also use several different methods to complete electronic informed consent, if applicable and necessary, that include the following: 1) REDCap electronic consent (e-consent) combined with a video discussion on software approved by IT Security) or 2) via MUSC's doxy.me system (teleconsent). As a last resort, we will also email the consent document to the participant or parent/guardian and conduct the informed consent via video chat. Participants can then email or mail the signed consent back to the research team if needed. Video chat functionality will only be used if all parties have the capability and will be on software approved by the IT Security team at MUSC.

E-consent via REDCap will be saved in a separate informed consent database. All doxy.me signed consent forms will be saved as PDF files within our study records. Using these systems, signatures on the consent form may be obtained electronically via REDCap/doxy.me. These procedures for consenting remote study participants have been established in prior studies at MUSC (e.g., Prot# 19201). In the case that participants mail back hard copies of the consent (in rare instances), those will be stored in locked file cabinets in the offices of research staff.

[figure not shown]
During the consent process birth certificate information will be collected from the participant (ie, first/middle/last name, birthdate, biological sex, and city/municipality of birth). This is in a separate REDCap file from data collection and is not part of our study data collection. This information is to be used solely for creating a Global Unique Identifier (GUID) for the NIMH Data Archive (NDA). This data is not transmitted to NDA but rather used in their online GUID Tool to create the GUID. The GUIDs created will be used as the participants' ID when submitting study data to the NDA. This is detailed in the consent form.

Informed consent is viewed as an ongoing process, so participants will be given the opportunity to ask questions about their participation throughout the course of the visit. The consent document will contain a thorough review of potential risks associated with participation, including breach of confidentiality and privacy concerns.

